The study will be an observational, cohort study. Participants will be pulled from a retrospective cohort of all patients with proximal humerus fracture dislocations who underwent operative fixation at Royal Columbian Hospital between January 2011 – July 2021. They will then be grouped by their dislocation directions to look at the development of AVN. Eligible patients will be given the option to consent to the study. This provisional consent will be obtained over the phone, in the form of a verbal agreement. During this agreement the patient will also receive an appointment time for them to come into the office. If agreeable, patients will be asked to come into the clinic to sign the Informed Consent Form, see their treating surgeon, and complete up-to-date radiographs and patient reported outcome measures (PROMs). These radiographs and PROMs will be used to assess AVN and overall function.

Study Population

Inclusion criteria

- Patients ≥ 18 years of age
- Patients who underwent operative fixation of proximal humerus fracture dislocation at Royal Columbian Hospital between January 2011 – July 2021
- Willing and able to consent and complete patient reported outcome measures
- Willing and able to follow the protocol and attend a follow-up visit
- Able to read and understand English or have an interpreter available

Exclusion Criteria

- Skeletally immature patients
- Patients with pathological fractures
- Patients who have had previous operative fixation of proximal humerus
- Patients treated non-operatively
- Patients presenting outside of the study duration window
- Participants treated by a non-participating surgeon
- Deceased patients
- Patients unable to complete patient reported outcome measures
- Patients declining to come back to the clinic for updated x-rays
- Dementia
- Incarceration

Methods

All patients deemed appropriate for study inclusion will be determined based on review of imaging conducted by an orthopedic attending, fellow, or resident to look for proximal humerus fracture dislocations. Patients eligible for study will be grouped based on direction of dislocation in one of four groups, anterior, posterior, varus and valgus. Both surgical and

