immediate postoperative protocols were left to discretion of attending surgeon, at the time of the initial surgery. However, the standard postoperative protocol included an initial follow-up for surgical site assessment and removal of sutures and/or staples. In addition, a period of restricted activity status was also left to discretion of attending surgeon.

Study Visit

Study participants will come back for one visit; this will be an observational visit to see how they are doing now. This exam will be conducted in the clinic at a minimum of 2 years postoperatively. Vascularity of the humeral head and union of the fracture will be assessed on anteroposterior and axial radiographs, while patient reported outcomes will be assessed using Constant and Disabilities of Arm, Shoulder and Hand (DASH) Scores.

The Constant Score (CS) is a 100-point scale (high scores = high level of function) composed of individual parameters looking at pain, activities of daily living (ADL), mobility, and measuring the strength of the affected shoulder.

The DASH is a 30-item questionnaire that looks at the ability of a patient to perform certain upper extremity activities. The DASH score ranges from 0 (no disability) to 100 (most severe disability).

Data Collection

Baseline

- Radiographs
 - Dislocation direction
 - Fracture type
- Patient Demographics (Chart Review)
 - Age
 - Gender
 - American Society of Anaesthesiologists (ASA) Score
 - Medical History
 - Social History
- Injury Characteristics
 - Side of injury
 - Mechanism
 - AO/OTA Classification

Surgical Treatment

- Radiographs
- Surgical Demographics
 - Date of surgery
 - Anaesthesia Type
 - Any Additional Procedures on the Injured Limb

Observational Visit

- Radiographs
 - AP, Lateral, and Axillary views
- Radiographic outcomes

- AVN Evidence
- Follow-up Demographics
 - Follow-up Period
 - Date of Last Follow-up
 - Quality of Reduction
 - Re-operations on the Injured Limb
- Patient reported outcomes (DASH, CS)

Outcomes

Primary Outcome Measure

The primary outcome measure is avascular necrosis of the proximal humerus, based on radiographic criteria. (Cruess Classification)

Secondary Outcome Measure

Patient-reported outcome measures will be collected at the one visit

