DASH	Developed to assess single or multiple musculoskeletal disorders affecting the upper limb. The DASH is a very commonly used outcome measure that is fully patient-administered and contains 30-questions designed to quantify physical disability and symptoms in individuals with upper limb disorders.
CS	The constant shoulder score is one of the most commonly used outcome measures to assess shoulder disorders. It combines subjective and objective measurements in the form of: pain, activities of daily living, strength, and range of motion to provide you with a final score out of 100.

Radiographic Parameters

A/P, Lateral, and Axillary views.

Statistics

Sample Size

Out of a possible 70 participants we hope to enrol around 56 (with approximately 14 in each of the 4 dislocation groups). This accounts for 20% of the participants of the total to either choose not to enrol or be unavailable due to their morbidity status.

Data Analysis

As this is an observational study with limited patient population and no specific time points to reference, all participants will have the chance to complete the follow-up visit at their leisure. For this reason, we do not foresee needing to exclude any patients for missed appointments. At

the follow-up visit each participant will be assessed for the presence of AVN in comparison to their dislocation direction. Descriptive statistics will be utilized and reported on and parametric analysis will be completed as appropriate.

Ethical Considerations

Potential Benefits

It is not known whether or not participants will gain any direct benefit from the study. It is possible that participants that come back may still be experiencing some pain or issues in their injured limb and want to see the surgeon to discuss potential management.

It is expected that the results of the study will contribute to the literature of shoulder fracture-dislocations and the development of AVN following this type of injury, and provide a possible indication for a large study in the future.

Potential Risks

As this is an observational cohort study there are no anticipated risks to participating in the study. Treatment has already occurred and all follow-up has been completed as per standard of care procedures. The only additional procedures that participants would need to take part in for the study are additional radiographs and the completion of one visit that includes completing PROMs.

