If participants choose to have the data collected about them destroyed, this will be respected to the fullest extent possible. However, there may be exceptions where the data is not able to be withdrawn, for example, where the data is no longer identifiable or where the data has been merged with other data. If the participant wishes to request the withdrawal of the data, they should let their surgeon and/or research team know.

Blinding

In order to maintain blinding in the study the initial x-rays, taken when the participant's presented to the emergency department, showing the dislocation direction, will be reviewed and assessed by a qualified individual that didn't perform the surgery. During the one-time follow-up visit the surgeon, who performed the participant's surgery, will assess the x-rays the participant had that day to look for any evidence of AVN. The surgeons will be blinded to the dislocation direction the participant experienced initially.

Ethics

The study protocol, case report forms, questionnaires, and the consent form will be submitted and approved by Fraser Health Research Ethics Board prior to study implementation.

The study will be conducted in accordance with the Tri-Council policy statement: Ethical Conduct for Research Involving Humans, the International Conference on Harmonisation Guidance E6: Good Clinical Practice E6: Consolidated Guidelines, applicable government regulations, and institutional research policies and procedures.

Publication/Presentations

Results from the study will be submitted for publication and presented at national conferences as fellow-ship research to influence future studies.

References

1. Schumaier, A. and B. Grawe, *Proximal Humerus Fractures: Evaluation and Management in the Elderly Patient*. Geriatr Orthop Surg Rehabil, 2018. **9**: p. 2151458517750516.
2. Greiner, S., et al., *Humeral head necrosis rate at mid-term follow-up after open reduction and angular stable plate fixation for proximal humeral fractures*. Injury, 2009. **40**(2): p. 186-91.
3. Hertel, R., et al., *Predictors of humeral head ischemia after intracapsular fracture of the proximal humerus*. J Shoulder Elbow Surg, 2004. **13**(4): p. 427-33.
4. Boesmueller, S., et al., *Risk factors for humeral head necrosis and non-union after plating in proximal humeral fractures*. Injury, 2016. **47**(2): p. 350-5.

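### AVN is read only from the film of the single late visit, so a humeral head replaced or removed for AVN before that visit cannot count towards the primary outcome

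*Protocol*

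**What the plan says.** The Outcomes section defines the endpoint: "The primary outcome measure is avascular necrosis of the proximal humerus, based on radiographic criteria", using the Cruess classification. Three other places in the protocol tie the reading to the single visit:

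- Study Design, on the up-to-date clinic films and questionnaires: "These radiographs and PROMs will be used to assess AVN and overall function".
- Statistics, Data Analysis, on the timing of the assessment: at "the follow-up visit each participant will be assessed for the presence of AVN in comparison to their dislocation direction".
- Blinding, on the operating surgeon's task at the visit: he or she "will assess the x-rays the participant had that day to look for any evidence of AVN".

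Study Visit gives the method, "Vascularity of the humeral head and union of the fracture will be assessed on anteroposterior and axial radiographs", and the timing, "This exam will be conducted in the clinic at a minimum of 2 years postoperatively". No latest date is set. Data Analysis says there are "no specific time points to reference, all participants will have the chance to complete the follow-up visit at their leisure".

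The list of data for the observational visit includes "Re-operations on the Injured Limb". It names no reason for re-operation and does not connect the item to AVN. Among the exclusion criteria, the only one about other surgery on the proximal humerus concerns earlier fixation. Surgery after the index fixation is not excluded. The Withdrawal section allows a withdrawing participant's most recent film to be assessed, but that provision does not extend to those who attend.

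**The concern.** The protocol wants AVN rates by direction of dislocation, and Study Design frames this as how AVN develops after the injury. That is a cumulative question. The rule instead captures AVN still visible in a retained head on one late film. A shoulder holding a prosthesis, or with the head removed, cannot be staged. If AVN was the reason the head was lost, the event happened but cannot be recorded.

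The background section itself expects both more AVN and more revision surgery in fracture dislocations, so the situation is plausible here. The time in which a conversion could occur is long and differs between participants. The losses fall on severe cases, so the AVN rate is pushed down. If conversions are more frequent in one direction group, that group would look better than it is, and the main comparison would be affected.

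**Working it through.** **Figure in the plan.** Sample Size gives 70 possible participants less 20%: 70 × 0.80 = 56, and 56 / 4 = 14 per direction group. This reproduces and is not in dispute. The protocol states no AVN rate, conversion rate or power, so what follows is illustration.

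**Inputs.** From the protocol: 14 per group, surgery from January 2011 to July 2021, and a visit at 2 years or later. Assumed: x, the true number with AVN in a group, and k, the number of those heads replaced or removed for AVN before the visit.

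**If such shoulders are dropped as ungradable.** Observed rate = (x − k)/(14 − k). Loss = x/14 − (x − k)/(14 − k) = k(14 − x)/[14(14 − k)].

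| x (true rate) | k | Observed | Loss, points |
|---|---|---|---|
| 2 (14.3%) | 1 | 1/13 = 7.7% | 6.6 |
| 2 (14.3%) | 2 | 0/12 = 0% | 14.3 |
| 5 (35.7%) | 1 | 4/13 = 30.8% | 4.9 |
| 5 (35.7%) | 2 | 3/12 = 25.0% | 10.7 |
| 5 (35.7%) | 3 | 2/11 = 18.2% | 17.5 |
| 8 (57.1%) | 1 | 7/13 = 53.8% | 3.3 |
| 8 (57.1%) | 2 | 6/12 = 50.0% | 7.1 |

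One or two conversions therefore cost 3.3 to 14.3 points across this range. The upper end needs both AVN heads in a group with x = 2 to have been replaced.

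**If such shoulders are scored as no AVN.** Observed rate = (x − k)/14. For x = 5 and k = 1, 2, 3 this gives 4/14 = 28.6%, 3/14 = 21.4% and 2/14 = 14.3%. Both readings of the rule understate AVN; this one does so more.

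**Comparison between groups.** Take two groups that both truly have 5/14. If three heads were replaced for AVN in one group only and scored as no AVN, the groups are observed as 35.7% and 14.3%, a difference made entirely by ascertainment.

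**Against sampling error.** The exact (Clopper-Pearson) 95% interval for 5/14 is 12.8% to 64.9%. The shifts above are smaller than that uncertainty. They all run in one direction, however, and a larger sample would not remove them.

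**Timing.** January 2011 to July 2021 is about 10.5 years. If all visits fall in the same calendar period (assumed, since visit dates are not given), time from surgery to visit runs from 2 to about 2 + 10.5 = 12.5 years.

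**The case against.** The best reply is that this is an unwritten handling rule rather than an error. Re-operations are collected, so the affected shoulders can be identified, and a statistical analysis plan could say how to count them. The outcome sentence names no film, the text in Blinding mainly says who reads which images, and nothing forbids using earlier films. AVN present at late follow-up is also a coherent target, if a narrower one. The analysis is mainly descriptive, and no power claim or decision threshold rests on the AVN rate. The size is wholly assumed, and the case report form, which is not shown, may already record the reason for re-operation.

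Much of this is fair as a limit on size and certainty. The documents do not show that any participant is affected, or that conversions differ by direction. It does not remove the point. Three separate sections place the AVN reading at the visit, and the only use of another film is reserved for withdrawal. Following the rule as written understates AVN whether these shoulders are dropped or scored as unaffected. The outcome definition and its source film are set in the protocol itself. A later analysis rule could repair this only if the reason for re-operation is captured, which the listed item does not specify.

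**Conclusion.** The concern holds and should be fixed; confidence is medium. As written, AVN that cost the head before the visit is lost from the primary outcome, and the resulting error in the AVN rate is always downward. Its size cannot be found from the documents. Under the assumed counts, one or two such heads in a group of 14 lower that group's rate by 3.3 to 14.3 points when dropped. Distortion of the comparison by direction is possible but depends on unequal conversion, for which the documents give no evidence.

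**What to change.** Define the primary outcome as AVN (Cruess stage) on the visit film, or conversion to arthroplasty or head removal since index fixation with AVN as the documented reason. Grade such conversions on the last film before revision where one exists; otherwise count them as AVN, stage unknown. Do not score earlier films for other participants, so that detection does not depend on how often each was imaged. Make sure the re-operation item captures reason and date, and keep dislocation direction hidden from whoever assesses AVN. Report conversions for AVN and for other reasons by direction group, and give the visit-film-only result as a sensitivity analysis.

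The cost is one sentence in the outcome definition, a check of one form item, chart review for re-operated participants only, and ethics review of any changed form. The sample size is unchanged.

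There are downsides. The added component relies on a reason for revision recorded outside the study's blinding, and it would still miss a necrotic head replaced for another stated reason. A pre-revision film may not exist for every case. An event with unknown stage is not a radiographic reading, which is why the visit-film-only result is kept alongside.

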As with all research that includes imaging there is a risk of incidental findings. However, this will be dealt with by the most responsible person, who in this case, will be the surgeon that is seeing the participant and assessing their radiographs.

Along with research there is also a risk of loss of confidentiality. Every possible step will be taken to ensure participant confidentiality.

Data Management

Data will be stored in a password protected excel spreadsheet on the FHA M-Drive. Participants will be de-identified and receive a unique study ID. There will be a separate, password protected excel spreadsheet that will house the participants name and their unique study ID. Only necessary study personnel will have access to it.

Confidentiality

All data will be identified using a unique number and letter system in the form of a participant number. This number (e.g. PHFD-001, PHFD-002, etc) will be the only identifiers used for identifying study participants. Most of the data will be electronic and housed in password protected servers in the FHA network on the remote drive. Any paper copies of the CRFs or consent forms will be kept secure in locked cabinets inside the locked research office. The project manager will authorize personnel to access the data only as necessary.

Withdrawal

As the study consists of one study visit we do not anticipate the need for withdrawal. However, participants may choose to withdraw from the study at any time, without any affect to their care of treatment. Withdrawal will include the option to withdraw and still have their last radiograph assessed for the study, or they can choose to have a complete withdrawal (if they haven't completed the study procedures yet). If the participant has completed the study procedures and they choose to withdraw then a discussion will be had about what will happen to the information about them already collected. Participants have the right to request the destruction of their information collected for the study, or they may choose to leave the study and allow the investigators to keep the information already collected.

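### The protocol claims that AVN is read blind to dislocation direction, but the named reader is the operating surgeon, so blinding of the primary outcome cannot be assured

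*Protocol*

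**What the plan says.** The primary objective relates the rate of humeral head AVN to the direction of dislocation. The primary outcome is "avascular necrosis of the proximal humerus, based on radiographic criteria. (Cruess Classification").

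The Blinding section says three things in sequence:

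- The emergency department films that show direction are to be "reviewed and assessed by a qualified individual that didn't perform the surgery".
- At the follow-up visit, the surgeon who performed the operation "will assess the x-rays the participant had that day to look for any evidence of AVN".
- The section then declares those same readers blind: "The surgeons will be blinded to the dislocation direction the participant experienced initially".

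Other sections describe the same surgeon's role. Under Study Design, participants come to clinic to "see their treating surgeon, and complete up-to-date radiographs and patient reported outcome measures". Under Potential Risks, the person responsible for incidental findings "will be the surgeon that is seeing the participant and assessing their radiographs". The cohort consists of patients "who underwent operative fixation at Royal Columbian Hospital between January 2011" and July 2021, so every participant had the fracture dislocation surgically fixed.

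**The concern.** The person declared blind to direction is the person who operated on the displaced joint. A statement of blinding needs a procedure that makes it true, and a surgeon cannot be blinded afterwards to something learned while treating the patient.

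This matters because AVN is a reader's radiographic judgement and direction is the variable across which it is compared. If a reader knows the direction and that knowledge shifts the call, misclassification can differ between direction groups and create or hide a difference. Even if no call is shifted, readers of the publication would credit the primary outcome with a safeguard that the procedure cannot guarantee.

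**Working it through.** **The plan's own figures.** Sample Size gives 70 possible participants and 20% non-enrolment: 70 × (1 − 0.20) = 56, and 56 / 4 = 14 per direction group. Both reproduce. The point changes neither.

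**What each stated measure protects.**

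| Provision (protocol section) | What it does | Does it hide direction from the AVN reader? |
|---|---|---|
| Direction classified by someone who did not operate (Blinding) | Keeps the recorded direction independent of the AVN reader | No: the reader treated the injury |
| AVN read on the visit-day films (Blinding) | Sets which films are graded | No: earlier knowledge remains |
| Cruess classification (Primary Outcome Measure) | Narrows the reader's discretion | No: a criterion is not a blind |
| "The project manager will authorize personnel to access the data only as necessary" (Confidentiality) | Controls access to study data | No: it does not concern the clinical record |
| Imaging review for eligibility by an attending, fellow or resident (Methods) | Identifies eligible patients | No: it is a further route to seeing direction, and operating surgeons are not excluded from it |

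No other section resolves the conflict.

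**Could time have done the blinding?** Surgeries start in January 2011 and the reference list includes a 2022 publication, so the earliest cases would be read at least about 2022 − 2011 = 11 years after surgery. At the other end, surgeries run to July 2021 and Study Visit sets a minimum of 2 years, so some reads could come about 2 years after surgery. Recall is plausible for some reads and doubtful for others.

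**Illustration of size. All error rates are assumed; none is in the protocol.** Give two groups the same true AVN rate p. Let f be the share of reads made with knowledge of direction, equal in both groups, and let the remaining reads share common error rates.

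- Apparent rate = p × Se + (1 − p) × (1 − Sp)
- Spurious difference = f × (rate A − rate B), because the reads made without knowledge cancel

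Mild effect (Se/Sp 0.85/0.90 in A, 0.80/0.93 in B), p = 0.20:
- A: 0.20 × 0.85 + 0.80 × 0.10 = 0.250
- B: 0.20 × 0.80 + 0.80 × 0.07 = 0.216
- Difference: 3.4 points at f = 1, 1.7 at f = 0.5, 0 at f = 0

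Stronger effect (0.90/0.85 in A, 0.75/0.95 in B), p = 0.20:
- A: 0.20 × 0.90 + 0.80 × 0.15 = 0.300
- B: 0.20 × 0.75 + 0.80 × 0.05 = 0.190
- Difference: 11.0 points at f = 1, 5.5 at f = 0.5, 0 at f = 0

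With 14 per group, 11.0 points is 0.110 × 14 = 1.5 patients and 5.5 points is 0.8 patients. The standard error of the difference in the stronger case at f = 1 is √[(0.300 × 0.700 + 0.190 × 0.810) / 14] = 0.161, about 16 points.

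Other assumptions give other values. With Se 0.95 in both groups, Sp 0.95 against 0.80, p = 0.10 and f = 1, the rates are 0.140 and 0.275, a difference of 13.5 points with a standard error of √[(0.140 × 0.860 + 0.275 × 0.725) / 14] = 0.151. If f differed by direction, the simple scaling by f would fail. The illustration shows possible scale only.

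**The case against.** The strongest reply is that the protocol does more than assert blinding. It separates classification of direction from the AVN reading and points the surgeon to the visit-day films. Many operations are years old, AVN is graded on a published classification, and the study is descriptive, with about 56 participants and sampling error larger than any illustrated bias.

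Much of this stands. The separation is useful and should be kept. Recall will have faded for some cases, and nothing shows that any AVN call was or will be shifted. But fading memory is uncontrolled and is not a procedure, and a standard error does not excuse a systematic error. The protocol also hopes to provide an indication for a larger study, where sampling error would shrink and differential misreading would not.

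Three stronger readings are tempting, and the documents support none of them:

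- *That the protocol has no blinding measure at all.* It states two. They do not reach the surgeon's earlier knowledge.
- *That every AVN read will be made with knowledge of direction.* The interval since surgery makes this uncertain, so a flat statement that the assessment was unblinded would also go too far.
- *That the AVN comparison is biased.* Neither the size nor the sign of a bias can be derived.

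Nor is this a complaint about detail left to an analysis plan. The protocol itself names the reader and asserts the blinding.

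**Conclusion.** The point holds as a conflict within the Blinding section. The section claims blinded assessment for the primary outcome and names a reader for whom that cannot be assured. Confidence in the conflict is high, because it rests on the protocol's own statements about who operated, who reads the films and who sees the participant. No effect on the results is demonstrated: it may be zero, and every illustrated value is below the standard error of a two-group difference at 14 per group. The case for changing the text rests on the unsupported claim. It should be fixed, but it does not invalidate the design.

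**What to change.** **Minimum.** Replace the sentence on surgeon blinding with wording such as: *Surgeons will not be given the study's direction classification and will read only that day's films; because they performed the surgery, blinding to dislocation direction cannot be assured.* Report this as a limitation of the primary outcome. The wording keeps the useful instruction to withhold direction, which simple deletion would lose. The cost is a short text edit. It corrects the claim but leaves any possible bias in place.

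**Preferable, where the existing participating surgeons allow.** The study's Cruess reading is made on the follow-up film, labelled with the PHFD number only, by a participating surgeon who did not:

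- operate on that patient,
- classify that patient's injury films, or
- screen that patient's imaging for eligibility.

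The treating surgeon still views the film for care and incidental findings. The cost is one short read per participant, about 56 in all, and some scheduling. Feasibility depends on the number of participating surgeons, which the protocol does not state. Because follow-up films may themselves hint at the injury pattern, the report should call this independent reading and not guaranteed blinding.
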